### 6.2.6 Turesky Modification of the Quigley Hein Index (TPI)

The TPI is a non-invasive assessment of supra-gingival plaque accumulation ([Turesky 1970](#), [Lobene 1986](#)). TPI will be assessed for all evaluable surfaces of the facial and lingual surfaces of the teeth (7-7 in each arch). Each tooth surface is divided into 3 areas; three scores are recorded facially (mesiofacial, facial, distofacial) and three scores lingually (mesiolingual, lingual and distolingual), generating six scores per tooth.

The plaque is first disclosed, as described in [Section 6.2.5](#), then each evaluable site is scored as follows:

Score	Description
0	No plaque

Property of Haleon- Confidential

May not be used, divulged, published or otherwise disclosed without the consent of Haleon

1	Slight flecks of plaque at the cervical margin of the tooth
2	Thin, continuous band of plaque (1 millimetre (mm) or smaller) at the cervical margin of the tooth
3	Band of plaque wider than 1mm but covering less than 1/3 of the area
4	Plaque covering at least 1/3 but less than 2/3 of the area
5	Plaque covering 2/3 or more of the crown of the tooth

### 6.2.7 Repeatability Assessments

Repeat MGI and TPI assessments will be performed by the clinical examiners at Visits 2 and 3. At least 3 subjects will be selected for repeat assessments over the duration of each of visit 2 and 3. Thus a total of at least 6 subjects repeat assessments for each endpoint will be collected during this study. ‘Repeat’ subjects will be selected at random from those in attendance on any given assessment day. Different subjects should be used for repeat MGI and TPI assessments.

There should be a delay of at least 10 minutes between the original and the repeat assessment for a given subject; ideally, repeat assessments should be separated by another subject. No other clinical procedure should be carried out on the selected subject between repeat assessments.

Scores from the first assessment must not be visible to the examiner/scribe when the repeat assessment is carried out.

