### **AT SCREENING (Visit 1)**

7. Subject with at least 20 natural, permanent teeth, (excluding 3rd molars).
8. Subject with at least 40 evaluable surfaces for MGI, BI, and TPI.

*An evaluable surface is defined as having 2/3rds of the natural tooth surface gradable for the selected clinical indices. The following should not be included in the evaluable surface count- third molars; fully crowned/extensively restored, grossly carious, orthodontically banded/bonded or abutment teeth; surfaces with calculus deposits which, in the opinion of the clinical examiner, would interfere with the baseline assessments of the selected clinical indices.*

9. A healthy subject with mild to moderate plaque-induced gingivitis in the opinion of the clinical examiner
10. Overall MGI  $\leq$  1.75 to  $\leq$  2.30

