## 5.2 Visit 1/Screening

Screening procedures will be conducted by the Investigator (or suitably qualified designee), prior to randomization to study product. Where practically feasible, they should be completed in the order listed below.

- 1) Informed consent
- 2) Demographics
- 3) Medical history and prior/concomitant medication/treatment
- 4) Review of subject's current oral care product
- 5) OST examination
- 6) OHT examination
- 7) Inclusion/exclusion criteria (including MGI and BPE)
- 8) Subject eligibility
- 9) Record Adverse Events.

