### **5.3 Visit 2/Day 1 (Baseline)**

- 1) Review of concomitant medication or non-drug treatments/procedures, adverse events, and lifestyle restrictions.
- 2) OST examination
- 3) **CCI** [REDACTED]
- 4) MGI assessment
- 5) BI assessment (including number of bleeding sites which is derived from BI assessment)
- 6) Plaque disclosure
- 7) TPI assessment
- 8) Inclusion/exclusion criteria
- 9) Subject eligibility
- 10) MGI repeatability assessment (where applicable)
- 11) TPI repeatability assessment (where applicable)
- 12) Subject is offered snack to consume
- 13) Prophylaxis tooth cleaning followed by confirmation of zero plaque by second clinician
- 14) RandomizationDispense study product, toothbrush, rinsing cups and oral hygiene instructions
- 15) Supervised brushing at site
- 16) **CCI** [REDACTED]
- 17) AE recording (if applicable)

Spontaneous reporting of adverse events and those elicited by asking subjects to respond to a non-leading question such as “How do you feel?” will be assessed any AEs recorded in the eCRF.

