## 6.2 Efficacy Assessments

The following efficacy assessments will be performed by appropriately trained staff/clinical examiners, at the times and in the order defined in the **STUDY PROCEDURES** section of this protocol.

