### 6.2.2 Modified Gingival Index (MGI)

The MGI is a non-invasive visual assessment of gingival inflammation ([Lobene 1986](#)).

MGI will be assessed for all evaluable surfaces of the facial and lingual/palatal gingiva, four sites per tooth (facial gingiva: papilla and margin; lingual/palatal gingiva: papilla and margin) and scored as follows.

Score	Description
0	Absence of inflammation
1	Mild inflammation; slight change in colour, little change in colour; little change in texture of any portion of the marginal or papillary gingival unit.
2	Mild inflammation; criteria as above but involving the entire marginal or papillary gingival unit.
3	Moderate inflammation; glazing, redness, oedema, and/or hypertrophy of the marginal or papillary gingival unit.
4	Severe inflammation; marked redness, oedema and/or hypertrophy of the marginal or papillary gingival unit, spontaneous bleeding, congestion, or ulceration.

Property of Haleon- Confidential

May not be used, divulged, published or otherwise disclosed without the consent of Haleon

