### 6.2.3 Bleeding Index (BI)

The BI is an invasive assessment of gingival bleeding ([Saxton and Van der Ouderaa 1989](#)). BI will be assessed for all evaluable surfaces of the facial and lingual/palatal gingiva, six sites per tooth (mesiobuccal, buccal and distobuccal; mesiolingual/palatal, lingual/palatal and distolingual/palatal) and scored as follows.

Score	Description
0	Absence of bleeding on probing
1	Bleeding observed within 30 seconds of probing
2	Bleeding observed immediately on probing

Sites with a score of 1 or 2 will be classified as 'bleeding' sites.

To perform the bleeding assessment, a round-end probe (e.g., CPITN\* probe) is inserted approximately 1 millimetre (mm) into the gingival sulcus (at approximately 60 degrees) and moved around the tooth from the distal interproximal area to the mesial interproximal area, gently stretching the gingival epithelium. Contact with the tooth surface should be avoided. Presence/absence of gingival bleeding is assessed for 30 secs after probing. Assessments should be performed one quadrant at a time, with BI scores recorded for the most recently probed quadrant before moving on to the next.

\*CPITN = Community Periodontal Index of Treatment Needs

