### 6.2.5 Plaque Disclosure Procedure

Dental plaque forms as a colourless deposit on the teeth and so requires ‘staining’ with disclosing solution prior to TPI assessment. The disclosing solution supplied by the sponsor will be used according to the manufacturer’s instructions.

At the request of the subject, to minimize staining of the lips, the clinical assessor may apply a thin layer of petroleum jelly to the subject’s lips as a barrier, prior to applying the disclosing solution.

Care should be taken to ensure no petroleum jelly comes into contact with the labial surfaces of the anterior teeth as this could impact TPI assessment for these surfaces.

Subject rinses with 10 mL tap water for 10 seconds and expectorates to remove any food debris from the mouth.

Disclosing solution will be dispensed into a dispensing cup (~2.5 ml) and subject rinses for 10 seconds to distribute this solution around their mouth. Care should be taken not to dislodge the plaque during this process.

Subject rinses with another 10 mL tap water for 10 seconds and expectorates to remove excess solution from the mouth.

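### The visit lists put BI probing, plaque disclosure and TPI between the first MGI and its repeat, where Section 6.2.7 and SAP 4.6.1 allow no procedure

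*Protocol*

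**What the plan says.** Protocol 6.2.7 asks for repeat MGI and TPI scoring in at least 3 subjects at each of Visits 2 and 3, using different subjects for the two indices. At least 10 minutes must separate the original reading from the repeat. It then adds: "No other clinical procedure should be carried out on the selected subject between repeat assessments". SAP 4.6.1 carries the same sentence.

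The visit lists are in protocol 5.3 (Visit 2) and 5.4 (Visit 3). In each, the line "MGI repeatability assessment (where applicable" comes after BI, plaque disclosure and TPI.

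Section 6.2, which contains 6.2.7, says efficacy assessments will be "performed by appropriately trained staff/clinical examiners, at the times and in the order defined in the" Study Procedures section. The only softening of a listed order is in Section 5.2, for Screening: "Where practically feasible, they should be completed in the order listed below". Sections 5.3 and 5.4 have no such wording.

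SAP 4.6.1 compares first and repeat scores with a Fleiss-Cohen weighted kappa and interprets the result as intra-examiner reliability. The bands are excellent above 0.75, fair to good from 0.4 to 0.75, and poor below 0.4. SAP 4.6.1.1 requires only that both readings of a tooth site exist at the same visit.

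**The concern.** For a subject chosen for the MGI repeat, the two instructions cannot both be followed. Keeping to the list breaks 6.2.7, and keeping to 6.2.7 departs from the list.

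The procedures in between act on the tissue that MGI scores. Section 6.2.2 states: "The MGI is a non-invasive visual assessment of gingival inflammation". The grades rest on colour, texture, redness and oedema of the marginal and papillary gingiva, and the top grade also includes spontaneous bleeding. In the BI examination of Section 6.2.3 a probe is placed about 1 mm into the sulcus and "moved around the tooth from the distal interproximal area to the mesial interproximal area, gently stretching the gingival epithelium". Section 3 declines to repeat BI at all because it is invasive. For disclosure, Section 6.2.5 has dye dispensed into a cup, and the "subject rinses for 10 seconds to distribute this solution around their mouth".

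A repeat MGI taken after these steps may differ from the first because the gingiva has changed or is stained, and not because the examiner was inconsistent. The kappa would then no longer measure examiner reliability alone. The SAP has no rule on order, so such pairs would enter Table 14.2.8.1 unmarked.

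**Working it through.** The plan gives no figure to reproduce on this point. The check compares the listed steps with the rule and then counts how much data could be involved.

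**Order of steps (protocol 5.3 and 5.4)**

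| Step | Visit 2 | Visit 3 |
|---|---|---|
| First MGI | 4 | 6 |
| BI | 5 | 7 |
| Plaque disclosure | 6 | 8 |
| TPI | 7 | 9 |
| Criteria and eligibility checks | 8, 9 | none |
| Repeat MGI | 10 | 10 |
| Repeat TPI | 11 | 11 |

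The eligibility checks are not clinical procedures. That leaves three clinical procedures between the first and repeat MGI at each visit: steps 5, 6 and 7 at Visit 2, and steps 7, 8 and 9 at Visit 3. Sections 6.2.7 and SAP 4.6.1 allow none.

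**TPI repeat.** The only listed clinical step between TPI and its repeat is the MGI repeat, which is done on different subjects. A subject chosen for the TPI repeat therefore has no clinical procedure in between, and the rule is met.

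**Inputs for the counts**
- Minimum surfaces, from the Screening inclusion criteria in Section 4.2: "Subject with at least 40 evaluable surfaces for MGI, BI, and TPI". This corresponds to 20 teeth with 2 surfaces each.
- Maximum teeth, from Section 3: 28 without third molars, so 28 x 2 = 56 surfaces.
- MGI, from Section 6.2.2: 4 sites per tooth, or 2 per surface.
- BI, from Section 6.2.3: 6 sites per tooth, or 3 per surface.
- Repeat subjects, from Section 6.2.7: at least 3 per visit, so at least 3 x 2 = 6.

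**Results**
- MGI site pairs per subject: 40 x 2 = 80 to 56 x 2 = 112.
- MGI site pairs for 6 subjects: 80 x 6 = 480 to 112 x 6 = 672.
- BI sites probed per subject before the repeat MGI, if the list is followed: 40 x 3 = 120 to 56 x 3 = 168. Every re-scored surface would have been probed at 3 sites.

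These counts describe exposure only. The documents give no basis for calculating a change in kappa.

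**The case against.** The strongest reply is that the lists need not be read as a strict sequence. Section 5 introduces them as procedures to complete, and 5.3 and 5.4 do not themselves demand an order. Table 5-1 arranges some items differently from the lists; for example, it shows inclusion and exclusion criteria above MGI, whereas 5.3 has them at step 8. The repeat lines apply only where relevant and sit together at the end of the assessment block. Section 6.2.7 is the dedicated text, so a trained examiner would probably follow it. This reading is reasonable, but the site has to infer it. Section 6.2 expressly ties its assessments to the listed order, while the row order of Table 5-1 is not a stated sequence.

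A second reply is that the harm is not demonstrated. That is correct. Neither an effect on kappa nor its direction is shown in the documents, nothing in the trial depends on the kappa bands, and repeat scores are kept out of efficacy. This limits the severity but does not remove the conflict.

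A third reply is that an out-of-order repeat would appear as a protocol deviation under SAP 4.1.2. A site that followed 5.3 or 5.4 as written would have little reason to log one, and Listing 16.2.2.2 covers randomized subjects only.

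The last reply is that a protocol edit needs ethics approval under Section 9.9.1. It does, but the edit can wait for another amendment.

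**Conclusion.** The inconsistency is real and certain from the text, and it is minor. Three clinical procedures are listed where the repeatability rule allows none, at both visits, and no passage says which instruction governs. The rule in 6.2.7 is sound; the visit lists are what do not match it.

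The consequence is conditional. If the site follows 6.2.7, the order raises no problem for the MGI kappa. If it follows the lists, the kappa may carry procedure effects as well as examiner error. Should such effects occur, they would probably lower kappa and understate the examiner's reliability, since a change in the tissue between readings adds disagreement that the examiner did not cause. That direction is a judgement, and no size is claimed.

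The reach is one descriptive table and at least 6 subjects. The primary BI result, the other efficacy analyses, the sample size and the TPI repeat are not affected.

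**What to change.** In protocol 5.3 and 5.4, move the MGI repeat line so that it falls at least 10 minutes after the first MGI and before BI. Alternatively, add one sentence to each list saying that Section 6.2.7 overrides the listed order for subjects selected for the MGI repeat. Leave the TPI repeat where it is.

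If any MGI repeat is known to have been done after BI or disclosure, say so in a footnote to Table 14.2.8.1. A kappa with and without such pairs is not requested. The SAP lists times for supervised brushing, but the documents do not say that times or sequence are recorded for MGI, BI or TPI.

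The cost is one line moved or one sentence added in each of two lists, bundled with another amendment. The change does not appear to call for an eCRF change, though the eCRF is not among the documents. Section 6.2.7 already requires the 10-minute gap; what is new is that it falls before BI. That is at least 6 x 10 = 60 minutes over the whole study, and more if another subject is examined in between, as 6.2.7 prefers. These subjects fast until their assessments are complete (Section 4.4.1), so the fast lengthens by the same wait. At Visit 2 a selected subject may later prove ineligible, but the pair still counts, because the MGI repeatability population in Section 8.2.1 does not require randomization.

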## 6.3 Safety and Other Assessments

The following safety assessments will be performed by appropriately trained staff/clinical examiners, at the times and in the order defined in the **STUDY PROCEDURES** section of this protocol.

### 6.3.1 Oral Soft Tissue (OST) Examination

The OST examination will be accomplished by direct observation and palpation, using retraction aids as appropriate. It will include examination of the labial mucosa (including lips), buccal mucosa, mucogingival folds, gingival mucosa, hard palate, soft palate, tonsillar area, pharyngeal area, tongue, sublingual area, submandibular area and salivary glands. The results of the examination will be recorded in the eCRF as either ‘normal’ or ‘abnormal’; the details of any abnormalities will be described in the eCRF.

Any OST observation that changes from ‘normal’ to ‘abnormal’, or worsens, from Screening will be recorded as an AE in the eCRF.

Property of Haleon- Confidential

May not be used, divulged, published or otherwise disclosed without the consent of Haleon

### **6.3.2 Oral Hard Tissue (OHT) Examination**

The OHT examination will be accomplished by direct observation, using retraction aids as appropriate. It will identify enamel irregularities, tooth fractures, grossly carious lesions/gross decay, defective/faulty restorations, direct & indirect restorations including fixed/removal prostheses, non-carious tooth surface loss (abrasion, attrition, abfraction and erosion), any other hard tissue irregularities (e.g., hypo/hypermineralisation, decalcification) and significant tooth staining. Conditions will be listed as 'absent' or 'present'; those noted as 'present' will be described in the eCRF. Any OHT observation that changes from 'absent' to 'present', or worsens, from Screening will be recorded as an AE in the eCRF.

The presence of implants, fixed or removable dentures, fixed or removable orthodontic braces/bands, fixed orthodontic retainers, full crowns or veneers will be recorded, along with evidence of gross intra-oral neglect or the need for extensive dental therapy.

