**CCI**

Within approximately 3-5 weeks (21-35 days) of Screening (Visit 1), eligible subjects will return to the site for the Baseline visit (Visit 2), with overnight plaque (subjects will be instructed to abstain from oral hygiene for 12 hours [+3 hours; -2 hours] i.e., overnight immediately before the visit). At the Baseline visit, concomitant medication and inclusion/exclusion criteria will be checked and then subjects will undergo a full OST examination, **CCI**, MGI, BI and TPI assessments.

Subjects will be considered eligible with a minimum of 20 natural teeth, at least 40 evaluable surfaces, overall  $MGI \geq 1.75$  and  $\leq 2.3$  and overall  $TPI \geq 1.5$ . Subjects with MGI and TPI score outside the study range will be discontinued from the study at this visit.

After **CCI** all initial clinical assessments, eligible subjects will receive a standardise snack followed by a full mouth dental prophylaxis to remove sub and supragingival calculus, stain, plaque and debris from the teeth. Post-prophylaxis, the subject's teeth will be re-disclosed, and a second clinician will check all plaque and calculus has been

Property of Haleon- Confidential

May not be used, divulged, published or otherwise disclosed without the consent of Haleon

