### 5.1 Schedule of Activities

**Table 5-1 Schedule of Activities**

The schedule of activities table provides an overview of the protocol visits and procedures.

The investigator may schedule visits (unplanned visits) in addition to those listed on the schedule of activities, in order to conduct evaluations or assessments required to protect the well-being of the subject.

Procedure/Assessment	Screening		Visit 2 Baseline Day 1	Visit 3 Week 4 Day 28 (± 2)
	Visit 1			
Informed Consent	X	Lead in period [approximately 3-5 weeks (21-35 days)]		
Demographics	X			
Medical History	X			
Current/Prior Medication Review	X			
Review subject's current oral care products	X			
Oral soft tissue (OST) examination	X		X	X
Oral hard tissue (OHT) examination	X			X
Inclusion/exclusion criteria	X		X	
Modified Gingival Index (MGI)	X 		X 	X
Basic Periodontal Examination (BPE)	X 			
BI (Bleeding index)			X	X

Property of Haleon- Confidential

May not be used, divulged, published or otherwise disclosed without the consent of Haleon

Haleon

Clinical Protocol

Protocol Number: 300178

CC1			X	X
Disclose dental plaque			X	X
Turesky Plaque Index (TPI) assessment			X	X
Subject eligibility	X		X	
Repeat MGI assessment 			X	X
Repeat TPI assessment 			X	X
Compliance Checks			X	X
Concomitant medications and treatments			X	X
Subject Continuance				X
Dental prophylaxis			X	
2 nd clinician check to confirm TPI=0 (additional dental cleaning will be performed as required)			X	
Randomization			X	
Dispense study product, toothbrush, rinsing cups and oral hygiene instructions			X	
Supervised brushing with study product			X	X
CC1			X	X
Subject brings study product, toothbrush for brushing on site				X
Visual inspection of study product to check compliance				X
Adverse Events (AEs) Review 	X		X	X
Optional dental prophylaxis at the end of Visit 3				X
Study Conclusion/Subject Exit from Study				X

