### **8.3.3 Safety Analysis(es)**

Safety analyses will be performed on the Safety population, according to investigational product received. AEs will be regarded as 'treatment emergent' if they occur on or after the first use of investigational product at Baseline. In the event of a missing start date, an AE will be assumed to be 'treatment emergent' unless the end date is prior to starting treatment. In case of misallocation, compared to the randomization schedule, TEAEs will be associated with the most recent study investigational received.

Property of Haleon- Confidential

May not be used, divulged, published or otherwise disclosed without the consent of Haleon

CCI

Abbreviated Clinical Protocol Template v1.0

Page 37 of 53

Haleon

Clinical Protocol

Protocol Number: 300178

Each AE will be categorized as oral or non-oral by the investigator or medically qualified designee. All will be reviewed by the CRS and coded using the MedDRA prior to database lock and unblinding.

A listing of all AEs will be presented for all subjects in the Safety population with the following AE summaries (number of distinct AEs and frequency/proportion of subjects affected) presented by treatment group and overall:

- TEAEs
- TEAEs by System Organ Class (SOC) and Preferred Term (PT)
- TEAEs by Oral/Non-Oral and PT
- Treatment emergent treatment related AEs by Oral/Non-Oral and PT
- Treatment emergent treatment related serious AEs by SOC and PT

Separate listings will be presented for:

- Deaths, SAEs and any AEs leading to product or study discontinuation.
- OST findings (with a summary of abnormalities by visit)

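### The oral-examination AE rules compare findings with Screening, not with the state just before first product use, so a finding that clears and returns on product triggers no AE under them, and a new Week 4 hard-tissue finding may be impossible to date

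*Protocol*

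**What the plan says.** The safety objective (Protocol Table 2-1, SAP Table 1-2) is oral tolerability over 4 weeks of use, with TEAEs as its endpoint.

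- **OST rule, Protocol 6.3.1:** "Any OST observation that changes from ‘normal’ to ‘abnormal’, or worsens, from Screening will be recorded as an AE in the eCRF".
- **OHT rule, Protocol 6.3.2:** a condition that goes from absent to present, "or worsens, from Screening will be recorded as an AE in the eCRF". The list of OHT items ends with "decalcification) and significant tooth staining".
- **Visit 2, Protocol Section 3:** before first brushing, subjects have a "full mouth dental prophylaxis to remove sub and supragingival calculus, stain, plaque and debris from the teeth".
- **Schedule, Protocol Table 5-1:** OST is done at Screening, Visit 2 and Week 4. OHT is done at Screening and Week 4 only. The lead-in lasts 21 to 35 days.
- **TEAE status:** Protocol 8.3.3 and SAP 4.5.1 both count from first product use at Visit 2. For a missing start date, Protocol 8.3.3 adds that "an AE will be assumed to be 'treatment emergent' unless the end date is prior to starting treatment".
- **Baseline, SAP 3.1:** the Day 1 pre-brushing value, for all endpoints.

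The SAP's table of changes to the protocol (Section 5) alters how OST and OHT findings are captured. It does not change the visit they are compared with.

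**The concern.** The endpoint is meant to capture change on product. The examination rules measure change from a visit 3 to 5 weeks before product use, and on the other side of a procedure that deliberately alters one of the listed findings. Two things follow.

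1. **A change on product can produce no AE under the rule.** This happens when the finding was there at Screening, was gone before first use, and came back no worse than at Screening.
2. **A hard-tissue change that predates the product may first be examined after 4 weeks of use.** Nothing in the scheduled OHT examinations then shows on which side of first use it arose.

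At stake is whether the TEAE counts describe the treatment period. Unrecorded recurrences lower the counts, and misdated hard-tissue findings raise them.

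**Working it through.** The plan gives no figure on this point, so there is none to reproduce. The check follows each type of finding through the visits and then does one interval calculation.

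**Step 1. Apply the rules to each pattern.**

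| Finding | Screening | Visit 2, before first use | Week 4 | AE required by 6.3.1 / 6.3.2? |
|---|---|---|---|---|
| OST, cleared and returned | abnormal | normal | abnormal, no worse than Screening | No: neither new nor worse than at Screening |
| Significant extrinsic stain | present | removed by prophylaxis | present, no worse than Screening | No: present at both reference points and not worse |
| OST, arose in lead-in | normal | abnormal | any | Yes, at Visit 2. Onset precedes first use, so SAP 4.5.1 makes it non-treatment-emergent |
| OHT, arose in lead-in or at prophylaxis | absent | no OHT scheduled | present | Yes. If no start date is recorded, 8.3.3 makes it treatment emergent |

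The first two rows are changes on product that the rules do not catch. The third row works as intended, because the OST is repeated at Visit 2. The fourth row is the dating problem, and it concerns OHT.

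**Step 2. Share of the OHT comparison interval that precedes product use.**

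Inputs:
- Lead-in L = 21 to 35 days (Protocol Section 3 and Table 5-1).
- Week 4 falls on Day 28 ± 2, so on Day 26 to Day 30. Counting from Day 1, treatment time T = 25 to 29 days, or 27 days for Day 28 exactly.

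Formula: pre-product share = L / (L + T).

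- Smallest: 21 / (21 + 29) = 21/50 = 42%.
- Largest: 35 / (35 + 25) = 35/60 = 58%.
- With Week 4 on Day 28: 21/48 = 44% to 35/62 = 56%.
- Whole interval: 21 + 25 = 46 days to 35 + 29 = 64 days.

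Suppose new hard-tissue findings arise at a constant rate, with no effect of product or prophylaxis. Then about half of those first seen at Week 4 would predate the product. That is an assumption; the documents give no rates.

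**The case against.** The case on the other side is substantial.

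- **The rules state what must be recorded; they do not bar anything else.** Protocol 9.2 defines an AE without reference to Screening, and 5.3 and 5.4 add spontaneous and elicited reports. This stands. A reader might infer that no recurrence at the Screening level can ever be a TEAE; the documents do not support that. What remains is that an examiner following 6.3.1 and 6.3.2 is told to compare with Screening, and the other routes depend on someone noticing and reporting.
- **OST recurrences remain visible.** SAP 4.5.2.1 tabulates OST abnormalities by visit and product (Table 14.3.4.1) and lists them. This stands for OST, though the table does not change TEAE counts. OHT has a listing only (SAP 4.5.2.2).
- **The 8.3.3 default needs a missing start date.** An investigator may supply an onset, and causality assessment (9.5.2) must weigh timing. At Visit 2 the teeth are also seen during plaque scoring and the second clinician's check, and AE recording closes the visit. This stands: misdating is possible but not automatic.
- **Misdated events fall in both arms.** A reader might infer that lead-in and prophylaxis changes bias the comparison against the test product. They arise before product use in two randomized groups, so they add similar background to both and mainly dilute any difference.
- **The stain case is narrow.** Exclusion 20i removes heavy stain, although only where it could interfere with plaque assessment. The gap needs an eligible subject whose stain is significant at Screening and significant again, but no worse, within about 4 weeks of prophylaxis.

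**Conclusion.** The point holds in limited form and is minor. The examination rules use a reference that does not match the plan's own Day 1 baseline and TEAE definition. As written, they require no AE for a soft-tissue abnormality or significant stain that is gone before first use and returns no worse than at Screening. Separately, a hard-tissue change from the lead-in or prophylaxis may first be examined at Week 4, and it defaults to treatment emergent if undated. Soft-tissue changes arising in the lead-in are not affected, because the Visit 2 OST captures them.

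The number of subjects involved cannot be derived from the documents. It would be wrong to say that every subject with a Screening abnormality is affected: a soft-tissue finding must first resolve and then recur at no more than its Screening level. The only size available is the 42% to 58% of the OHT comparison interval that lies before the product, and reading it as a share of findings needs the constant-rate assumption. Stain recurrence could differ between arms if the products differ in staining, but no rate is given. TEAEs are summarized descriptively and success depends on BI alone, so the efficacy conclusion is untouched.

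**What to change.** 1. **Protocol 6.3.1:** for findings after first product use, compare with the most recent OST before first use, which is the Visit 2 examination. Keep Screening as the reference for findings at Visit 2.
2. **Protocol 6.3.2:** take extrinsic stain as absent once the Visit 2 prophylaxis is complete, so that significant extrinsic staining at Week 4 counts as a change. Keep the existing significance threshold, so that trivial stain does not become an AE.
3. **eCRF guidance:** for each new Week 4 OHT finding, have the examiner record an estimated onset (before, at or after the Visit 2 prophylaxis). Use the 8.3.3 default only when onset cannot be judged.
4. **Alignment:** state these references consistently with SAP 3.1, SAP 4.5.1 and Protocol 8.3.3.

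The cost is wording in the protocol, the SAP and the eCRF guidance, plus slightly more AE records. No examination is added. Two limits remain. An onset judged at Week 4 is weaker evidence than an OHT at Visit 2 would be. Also, the Visit 2 OST comes before the prophylaxis (5.3, steps 2 and 13), so a soft-tissue change caused by the prophylaxis still relies on the AE recording at the end of that visit.
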